Statistical Power Considerations in Building Better Caregiver Study

Study: R01 AG057855-01
PI: [name]
Date: 11 August 2019
NCT04428112

This document is a response to the DSMB recommendation: "The study team should provide a written explanation and revision to account for the changes in power calculations, particularly regarding drop-out rates."

Summary from study team. The statistical power consideration was revised based upon updated information on the challenges in the recruitment and retention provided by the study team. The study team, which includes the study biostatistician, has selected the randomization approach "*Varying (flexible) randomization ratio (1:1, 2:1, 3:1)*" described below based on changes in expected retention and power calculations also described below.

The original statistical power consideration was based on 1:1 randomization to treatment and control. Assuming 70% retention rate, 448 caregivers at the end of the study will allow us to detect an effect size of 0.265 in the primary outcome PHQ-8 depression symptoms score with a power of 0.80 at a significance level of 0.05 (two-sided). The effect size of 0.265 corresponds to about 1.5 difference in PHQ-8 score (range 0-24) between groups assuming a common standard deviation of 5.6 (Lorig K, Thompson-Gallagher D, Traylor L, et al. Building Better Caregivers: a pilot online support workshop for family caregivers of cognitively impaired adults. *Journal of Applied Gerontology*. 2012;31:423-437.)

The recruitment and retention challenge came to light based on new information from the accumulated experience with the VA BBC workshop, which has enrolled over 5,000 Veteran caregivers. Unpublished data made available to the study team demonstrates that if caregivers' respective assigned workshops do not start within 2 weeks, they quickly lose interest and do *not* attend the workshops. This new data prompted the current study team to reconsider the recruitment, randomization, and retention plan. The study team recognized that if study enrollment could not accrue fast enough to fill both a workshop group and attention control group within a 2-week period (i.e., total of 54 participants per 2-week period) at 1:1 randomization, then retention would drop precipitously similar to what has been documented for some VA caregivers. The new data suggest that the original 1:1 randomization plan may lead to a retention rate of 50%, and 320 caregivers at the end of study will provide a power of 0.66 to detect the same effect size of 0.265.

The revised statistical power consideration was based on randomization with ratios of 1:1, 2:1 or 3:1 to treatment and control, depending on the actual recruitment process of participants within each 2-week period of recruitment. The 2:1 and 3:1 randomizations are expected to help with the recruitment and retention.

Fixed randomization ratio (2:1, 3:1)

Assuming that a fixed ratio of 2:1 will be used in randomization and the retention rate will increase from 50% to 75%, then the sample size of 480 caregivers (320 in treatment and 160 in control) at the end of the study will provide us a power of 0.78 to detect the same effect size of 0.265.

Assuming that a fixed ratio of 3:1 will be used in randomization and the retention rate will increase from 50% to 75%, then the sample size of 480 caregivers (360 in treatment and 120 in control) at the end of the study will provide us a power of 0.71 to detect the same effect size of 0.265.

Varying (flexible) randomization ratio (1:1, 2:1, 3:1)

If enough caregivers are enrolled in a 2-week period (e.g., 54) to use a 1:1 randomization, that will be used; if there are somewhat fewer (e.g., 41), 2:1 randomization will be used; if fewer (e.g., 36), 3:1 randomization will be used. Use of this flexible approach has achieved high retention rates in the prior trials (e.g., Lorig KR, Sobel DS, Stewart AL, et al. Evidence suggesting that a chronic disease self-management program can improve health status while reducing hospitalization: a randomized trial. *Medical care* 1999;37:5-14). Assuming that the

randomization with varied ratios will increase the retention rate from 50% to 75% and the randomization ratio will be controlled for as a categorical variable in the analysis model, 480 caregivers at the end of the study will allow us to detect a partial correlation of 0.13 between the treatment and outcome with a power of 0.82 at a significance level of 0.05 (two-sided).

Randomization plan	Total sample size	Retention rate	# participants at the end of the study	Power	Effect size
Original 1:1	640	70%	448	0.80	0.265 (a treatment group difference of 1.5 in PHQ-8 score)
Original 1:1 but with revised downward estimate of retention based on new information from VA	640	50%	320	0.63	0.265
Fixed 2:1	640	75%	480	0.78	0.265
Fixed 3:1	640	75%	480	0.71	0.265
Varying 1:1, 2:1, 3:1	640	75%	480	0.82	A partial correlation of 0.13 between treatment and PHQ-8 score.

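### The DSMB power table prints 0.63 where its own text has 0.66, and gives the selected flexible plan's 0.82 on a different effect scale from the other four rows

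*Protocol*

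**What the plan says.** The Protocol document is a memo answering a DSMB request to explain the changed power calculations. Its *Summary from study team* says the flexible 1:1, 2:1 or 3:1 plan was selected "based on changes in expected retention and power calculations also described below".

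- **50% retention under 1:1.** The text says "320 caregivers at the end of study will provide a power of 0.66 to detect the same effect size of 0.265". The table row labelled "Original 1:1 but with revised downward estimate of retention based on new information from VA" has the same inputs (640 enrolled, 50%, 320 completers, 0.265) but prints power 0.63.
- **Fixed ratios.** With 480 completers at 0.265, the memo gives 0.78 for 2:1 (320/160) and 0.71 for 3:1 (360/120).
- **Flexible plan.** The text under *Varying (flexible) randomization ratio* claims enough power to "detect a partial correlation of 0.13 between the treatment and outcome with a power of 0.82 at a significance level of 0.05", with the ratio adjusted for as a categorical variable. The table's effect-size cell reads "A partial correlation of 0.13 between treatment and PHQ-8 score", where the four rows above it have 0.265.
- **Mix of ratios.** The ratio is set "depending on the actual recruitment process of participants within each 2-week period of recruitment". The memo gives 54 enrolled as an example for 1:1, then "if there are somewhat fewer (e.g., 41), 2:1 randomization will be used; if fewer (e.g., 36), 3:1 randomization will be used". It states no expected mix and no conversion between 0.13 and 0.265.

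**The concern.** There are two faults in one table.

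First, one scenario carries two power values. It is the scenario that prompted the redesign, so the DSMB should see a single correct figure for it.

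Second, the Power column invites a ranking. As printed, the selected plan (0.82) beats fixed 3:1 (0.71), fixed 2:1 (0.78) and the original plan at 70% retention (0.80), and it is the only revised option above 0.80. But 0.82 refers to a different effect. A partial correlation between treatment and outcome depends on the allocation as well as on the group difference: the more unequal the arms, the larger the difference that corresponds to 0.13. Part of the printed lead over 3:1, and possibly all of the lead over 2:1 and over 0.80, may come from the change of scale.

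**Working it through.** **Inputs from the memo.** Two-sided 0.05; d = 0.265; SD 5.6; completers 448, 320 and 480; arm sizes as stated; partial r = 0.13; ratio as a categorical covariate. The mix of ratios is not given, so it is varied.

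**1. Rows at d = 0.265.** Noncentral t with df = n1 + n2 − 2 and ncp = d·√(n1·n2/(n1+n2)):

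| Plan | Arms | ncp | Recomputed | Memo |
|---|---|---|---|---|
| 1:1, 70% | 224/224 | 0.265·√112 = 2.805 | 0.799 | 0.80 |
| 1:1, 50% | 160/160 | 0.265·√80 = 2.370 | 0.657 | 0.66 text, 0.63 table |
| Fixed 2:1 | 320/160 | 0.265·√106.67 = 2.737 | 0.780 | 0.78 |
| Fixed 3:1 | 360/120 | 0.265·√90 = 2.514 | 0.708 | 0.71 |

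Every figure reproduces except 0.63. For 160 per arm, the normal approximation gives 0.659, d = 1.5/5.6 = 0.268 gives 0.666, d = 0.27 gives 0.673 and a one-sided test gives 0.766. Power of 0.63 would need about 300 completers (150/150 gives 0.628).

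**2. The flexible row on its own scale.** f² = 0.13²/(1 − 0.13²) = 0.0169/0.9831 = 0.01719. The noncentrality is 480 × 0.01719 = 8.25 on 1 and 476 df, and power is 0.818. The memo's 0.82 is right for r = 0.13.

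**3. Converting r to d.** Let m be the completer-weighted mean of p(1−p), where p is the share allocated to treatment: 0.25 at 1:1, 0.2222 at 2:1, 0.1875 at 3:1. Taking 5.6 as the SD within ratio strata, r/√(1−r²) = d·√m. For r = 0.13 the left side is 0.1311, so:

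- all 1:1: d = 0.1311/0.5000 = 0.262 (× 5.6 = 1.47 PHQ-8 points)
- all 2:1: d = 0.1311/0.4714 = 0.278 (1.56 points)
- all 3:1: d = 0.1311/0.4330 = 0.303 (1.70 points)

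**4. The flexible plan at d = 0.265.** ncp = 0.265·√(480m), df = 480 − 1 − number of ratios used:

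| Completers in 1:1/2:1/3:1 cohorts (assumed) | m | Power |
|---|---|---|
| all 1:1 | 0.2500 | 0.826 |
| 70/20/10 | 0.2382 | 0.807 |
| 50/25/25 | 0.2274 | 0.789 |
| proportional to 54/41/36 | 0.2241 | 0.783 |
| 25/25/50 | 0.2118 | 0.760 |
| all 3:1 | 0.1875 | 0.708 |

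The 54/41/36 line assumes each ratio is used in equally many periods, with the memo's example cohort sizes and equal retention.

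**5. What remains of the printed leads at 54/41/36.**

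- Over fixed 3:1: 0.783 − 0.708 = 0.075 (printed 0.11).
- Over fixed 2:1: 0.783 − 0.780 = 0.003 (printed 0.04).
- Over the original plan: 0.783 − 0.799 = −0.016 (printed +0.02).

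**6. Break-even points.** Write a and c for the 1:1 and 3:1 shares.

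- Against fixed 2:1: m − 2/9 = (4a − 5c)/144, so the flexible plan wins only if a > 1.25c.
- Against the original plan: the same ncp needs m = 112/480 = 0.2333, that is 4a − 5c > 144 × (0.2333 − 0.2222) = 1.6. With no 3:1 cohorts at all, 1:1 cohorts must supply more than 40% of completers.

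**7. Sensitivity.** With d = 0.268 the limits are 0.72 and 0.83, and 54/41/36 gives 0.79.

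**The case against.** The misprint is not in dispute. The case against the second point is that 0.82 is arithmetically correct and its metric is openly labelled in text and table, so only a presentational request remains. Rounding matters too: d = 0.265 is r = 0.128 at 70/20/10 and 0.1254 at 50/25/25, both of which print as 0.13. The 3:1 and 2:1 values at 480 completers are already in the table. The example cohort sizes are not expected shares, and retention, not power, mainly drove the choice of plan.

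Much of this is fair. The 0.82 is not a miscalculation, and results for any particular mix are illustrations. But rounding does not rescue the comparison. The memo's power was evaluated at 0.13 itself, so at 50/25/25 power at 0.265 is still 0.789; and at 54/41/36, d = 0.265 is r = 0.1245, which prints as 0.12. The limits 0.71 and 0.83 need no assumption about the mix. The fixed-ratio rows do supply the lower limit, but nothing tells the reader to use them that way, and the upper limit is absent. The memo also names power as a basis for selection, and power is what the DSMB asked about.

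**Conclusion.** Both points hold.

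The 0.63 in the table is wrong. The text's 0.66 is right (0.657), so the error is about 0.03.

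The flexible plan's 0.82 is valid for a partial correlation of 0.13 but is not comparable with the other rows. At 0.265 the plan has power between 0.71 and 0.83. For the illustrative mixes of all three ratios it is 0.76 to 0.81, so 0.82 is about 0.01 to 0.06 too high as a figure on the table's common scale. Whether the plan beats fixed 2:1 or reaches 0.80 depends on a mix the memo does not state.

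The choice of plan survives on the memo's retention assumptions. Every mix exceeds the 0.66 of the 50% retention case, and any mix that includes 1:1 or 2:1 cohorts exceeds fixed 3:1. These figures are two-group calculations on completers, like the memo's own. They also assume 480 completers whatever the mix, and that 5.6 is the SD within ratio strata.

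**What to change.** 1. In the 50% retention row of the table, change 0.63 to 0.66.
2. In the flexible row and the matching sentence, report power at effect size 0.265 as a range: 0.71 if all cohorts are 3:1, to 0.83 if all are 1:1.
3. Attach the assumed mix to any single value. For example: 0.78 if each ratio is used in equally many periods, with cohorts of 54, 41 and 36 and equal retention.
4. If the partial correlation of 0.13 is kept, print its effect-size equivalents beside it (0.262 at 1:1, 0.278 at 2:1, 0.303 at 3:1) and state that they assume an SD of 5.6 within ratio strata.

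The cost is two table cells and one sentence. The stated power of the selected plan becomes a range, slightly less favourable for most mixes. Sample size, design and analysis do not change.

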## 4.0

## Initial Screening Questions

Updated June 2017

### 4.1 \* PROJECT SUMMARY: (REQUIRED) Give a brief overview of this project (250 words or less). Tell us what this study is about, who is being studied, and what it aims to achieve. If you have an NIH Abstract, paste it here: Click on the orange question mark to the right for more detailed instructions.

Among 13 million informal caregivers of individuals with Alzheimer's disease or related dementias, an estimated 1.4 million live in rural areas of the US. These caregivers are a vulnerable group due to their physical isolation and well-documented rural disparities in health care access and quality. Many rural dementia caregivers experience serious health consequences due to caregiving responsibilities that can limit their ability to maintain their caregiving role. Thus, there is an pressing need for effective, scalable, and accessible programs to support rural dementia caregivers so that they can sustain their own well-being and effective caregiving within the home environments of their loved ones.

Online programs offer a convenient and readily translatable option for program delivery because they can be accessed by caregivers in the home environment and at the convenience of the user. *Building Better Caregivers* is an online 6-week, interactive, small-group self-management, social support, and skills-building workshop developed for caregivers of individuals with Alzheimer's disease or related forms of dementia. In our evaluations of the program in non-randomized studies, caregivers experienced significant improvements in stress, depression symptoms, and self-efficacy and partners experienced improved well-being.

Building on these encouraging preliminary findings, we now propose to conduct a hybrid effectiveness-implementation randomized controlled trial that will enroll and randomize 640 rural dementia caregivers into two groups: 320 in the intervention (workshop) group and 320 in the

attention control group. Caregivers will be recruited through 19 community organizations (serving rural communities in 17 states). Primary outcomes will be caregiver stress and depression symptoms. We hypothesize that stress scores and depression symptoms will be significantly improved at 12 months in the intervention group versus control group. We will also identify key strengths (facilitators) and weaknesses (barriers) of workshop implementation. We will use the RE-AIM implementation framework and a mixed methods approach to identify implementation characteristics pertinent to both caregivers and rural community organizations.

If the *Building Better Caregivers* workshop is proven to be effective, this research has the potential to open new research horizons, particularly on how to reach and effectively support isolated dementia caregivers in rural areas with an intervention that is scalable, even in low-resourced settings. If the workshop can achieve its goals with rural dementia caregivers, some of those most isolated, it would also be expected to be scalable in other low-resourced settings (e.g., in urban or suburban environments).

#### 4.2 \* HUD DEVICE: (REQUIRED) Does this application involve a Humanitarian Use Device (HUD):

- No
- Yes, and it includes a research component
- Yes, and it involves clinical care ONLY

#### 4.3 \* TYPE OF RESEARCH: (Click the Help link for definitions and guidance): (REQUIRED)

- Biomedical research
- Social, behavioral, educational, and/or public policy research
- Hybrid - includes aspects of BOTH types of research (check this option if your research is mainly social/behavioral but also involves specimen collection or blood draws to look at biological measures)

#### 4.4 \* SUBJECT CONTACT: (REQUIRED) Does this study involve ANY contact or interactions with participants:

- Yes (including phone, email or web contact)
- No (limited to medical records review, biological specimen analysis, and/or data analysis)

#### 4.5 \* RADIATION EXPOSURE: Does your protocol involve any radiation exposure to patients/subjects EITHER from standard care OR for research purposes (e.g., x-rays, CT-scans, DEXA, CT-guided biopsy, radiation therapy, or nuclear medicine including PET, MUGA or bone scans): (REQUIRED)

- Yes
- No

#### 4.6 \* RISK LEVEL: (REQUIRED) What is your estimation of the risk level, including all screening procedures and study activities (Help Text updated 9/13):

- Minimal risk
- Greater than minimal risk

#### 4.7 \* REVIEW LEVEL: (REQUIRED) Requested review level (Click on the orange question mark to the right for definitions and guidance):

- Full Committee
- Expedited
- Exempt

**4.8 \* EXPEDITED REVIEW CATEGORIES: (REQUIRED)** If you think this study qualifies for expedited review, select the **regulatory categories** that the research falls under: (check all that apply)

- Category 1: A very limited number of studies of approved drugs and devices
- Category 2: Blood sampling
- Category 3: Noninvasive specimen collection (e.g. buccal swabs, urine, hair and nail clippings, etc.)
- Category 4: Noninvasive clinical procedures (e.g. physical sensors such as pulse oximeters, MRI, EKG, EEG, ultrasound, moderate exercise testing, etc.)
- Category 5: Research involving materials (data, documents, records, or specimens) that were previously collected for either nonresearch or research purposes
- Category 6: Use of recordings (voice, video, digital or image)
- Category 7: Low risk behavioral research or research employing survey, interview, oral history, focus group, program evaluation, human factors evaluation, or quality assurance methodologies

**4.11 \* CLINICAL TRIAL: (REQUIRED)** Is this a clinical trial? According to The World Health Organization (WHO) and the International Committee of Medical Journal Editors (ICMJE) a clinical trial is:

- Any research study that prospectively assigns human participants or groups of humans to one or more health-related interventions to evaluate the effects on health outcomes.

ICMJE requires registration of a clinical trial in a public database (such as ClinicalTrials.gov) prior to enrollment, for eventual publication of results in member biomedical journals. Guidance: Public Law 110-85 requires that all investigators who perform an *applicable clinical trial* must ensure that the trial is registered on a government web site called ClinicalTrials.gov. The FDA requires registration for "applicable clinical trials," defined as follows:

- For any trials of drugs and biologics: controlled clinical investigations, other than Phase 1 investigations, of a product subject to FDA regulation.
- For trials of biomedical devices: controlled trials with health outcomes of devices subject to FDA regulation, other than small feasibility studies, and pediatric post-market surveillance.

For additional information on the ClinicalTrials.gov registration process at UCSF and the definition of a clinical trial for purposes of registration, visit the ClinicalTrials.gov section of the UCSF Clinical Research Resource HUB.

Yes  No

### Clinical Trial Registration

"NCT" number for this trial:

pending

If you don't yet have the NCT#, type 'Pending.'

**4.12 \* CLINICAL TRIAL PHASE (REQUIRED)** Check the applicable phase(s) (Help Text updated 9/13):

- Phase I
- Phase II
- Phase III
- Phase IV

**4.13 \* INVESTIGATOR-INITIATED: (REQUIRED)** Is this an investigator-initiated study:

Yes  No

**4.14 \* CANCER: (REQUIRED)** Does this study involve cancer (e.g., the study involves patients with cancer or at risk for cancer, including behavioral research, epidemiological research, public policy

**research, specimen analysis, and chart reviews):**

Yes  No

If you don't know if you should answer 'Yes' or 'No,' please [email](#) the Cancer Center's Protocol Review Committee for help.

**4.15 SCIENTIFIC REVIEW: If this study has undergone scientific or scholarly review, please indicate which entity performed the review (check all that apply):**

- Cancer Center Protocol Review Committee (PRC) (Full approval is required prior to final CHR approval for cancer-related protocols.)
- CTSI Clinical Research Services (CRS) Advisory Committee
- CTSI Consultation Services
- Departmental scientific review
- Other:

\* Specify Other: **(REQUIRED)**

National Institute of Health of Health Center for Scientific Review Special Emphasis Panel: Health Disparities in Caregiving for Alzheimer's Disease

**4.17 \* FINANCIAL INTERESTS: (REQUIRED) Do you or any other responsible personnel (or the spouse, registered domestic partner and/or dependent children thereof) have **financial interests** related to this study:**

Yes  No

## 5.0 Funding

**5.1 \* FEDERAL FUNDING: (REQUIRED) Is this study currently supported in whole or in part by **Federal funding, even by a subcontract**, OR has it received **ANY** Federal funding in the past:**

Yes  No

The IRB is required to compare the grant to the IRB application for studies with federal support. Indicate which portion of your grant you will be attaching:

- For NIH grants, the Research Plan, including the Human Subjects Section
- For other federal proposals (contracts or grants), the section of the proposal describing human subjects work
- The section of your progress report if it provides the most current information about your human subjects work
- The grant is not attached. The study is funded by an award that does not describe specific plans for human subjects, such as career development awards (K awards), cooperative agreements, program projects, and training grants (T32 awards) OR UCSF (or the affiliate institution) is not the prime recipient of the award

**5.2 \* DoD INVOLVEMENT: Is this project linked in any way to the Department of Defense (DoD): (REQUIRED)**

Yes  No

**5.3 SPONSORS: Identify all sponsors and provide the funding details. If funding comes from a Subcontract, please list only the Prime Sponsor:**

## External Sponsors:

View Details	Sponsor Name	Sponsor Type	Awardee Institution:	Contract Type:	Project Number	UCSF RAS System Award Number ("A" + 6 digits)
No Sponsor has been added to this IRB Study						

If the funding is coming through UCSF and you don't know the A or P number, you can search the eProposal side for the contract or grant (this does NOT replace adding the sponsor by name above **AND** entering the A or P number):

Project Status	Proposal Number	Project Title	Principal Investigator
No Projects are Linked to this IRB Study			

## Other Funding Sources and Unfunded Research - Gift, Program, or Internal Funding (check all that apply):

- Funded by gift (specify source below)
- Funded by UCSF or UC-wide program (specify source below)
- Specific departmental funding (specify source below)
- Unfunded (miscellaneous departmental funding)
- Unfunded student project

#### 6.2 LOCATIONS: At what locations will study visits and activities occur:

Community organizations will be engaged in all phases of the project via a longitudinal webinar- and list-serve-based Learning Collaborative. The confirmed sites include: California Center for Rural Policy, Humboldt Independent Practice Association, Elder Options, Eastern Idaho Community Action Partnership, Bluegrass Area Agency on Aging and Independent Living, Maine Health, MAC Incorporated (Maintaining Active Citizens), Elder Services of the Merrimack Valley, Inc., University of Nebraska Medical Center (UNMC) College of Nursing, Centralina Area Agency on Aging, North Carolina Department of Health and Human Services, Division of Aging and Adult Services, South Dakota State University, North Central Texas Council of Governments, Area Agency on Aging of North Texas, Area Agency on Aging of the Panhandle, Area Agency on Aging of Tarrant County, Texas A&M Center for Population Health and Aging, Wisconsin Institute for Healthy Aging, and Wyoming Center on Aging, University of Wyoming.

Study participants will be recruited through 19 community organizations (serving rural communities in 17 states). They will provide input on recruitment approaches and will provide organization preferences and suggestion for recruitment of the rural caregivers they serve. All centers have agreed to help with recruitment efforts by distributing flyers, posting flyers, mailings, brochures, radio ads, list-serve, etc.

Intervention group participants: will access the Building Better Caregivers 6-week program online at home. The workshop platform has the capability to track user engagement data such as number of workshop log-ins, website sections visited, number of postings/messages, action plans made and completed, and workshop completion.

Control group participants: will receive a mailed educational packet and two brief staff phone calls.

Survey data will be collected through online surveys completed by caregivers and conducted at baseline, post-intervention (1.5 months), and 6, and 12 months using the secure REDCap application. We will also give participants the option to complete questions by mail or phone interview.

